3.4. Multiple Comparisons

Adjustments for multiplicity will not be made, because no formal statistical testing will be performed in this study.

3.5. Missing Data and Outliers

3.5.1. Missing Data

Missing data can have an impact upon the interpretation of the trial data. In general, missing data will not be imputed unless methods for handling missing data are specified as follows.

- A missing pre-treatment laboratory result would be treated as normal (ie, no toxicity grade) for the laboratory abnormality summary.
- For missing last dosing date of study drug, imputation rules are described in Section 4.2. The handling of missing or incomplete dates for AE start is described in Section 7.2.6.2, and for prior and concomitant medications in Section 7.5.
- Missing PK sampling dates may be imputed based on other visit information. Missing PK sampling times may be imputed to nominal times. Missing drug concentrations will not be imputed.
- All available data for participants who do not complete the study will be included in the data listings.

3.5.2. Outliers

Outliers of non-PK data will be identified during the data management and data analysis process, but no sensitivity analyses will be conducted. All data will be included in the data analysis.

Outliers of PK data may be identified during review of data by the PK scientist, and if necessary, appropriate sensitivity analyses may be conducted.

3.6. Data Handling Conventions and Transformations

3.6.1. Data Handling Conventions and Transformations for Non-PK Data

The following conventions will be used for the imputation of date of birth when it is partially missing or not collected:

- If only month and year of birth is collected, then “15” will be imputed as the day of birth.
- If only year of birth is collected, then “01 July” will be imputed as the day and month of birth.
- If year of birth is missing, then date of birth will not be imputed.

In general, age collected at Day 1 (in years) will be used for analyses and presented in listings. If age at Day 1 is not available for a participant, then age derived based on date of birth and the Day 1 visit date will be used instead. If an enrolled participant was not dosed with any study drug, the enrollment date will be used instead of the Day 1 visit date. For screen failures, the date the first informed consent was signed will be used for the age derivation. Age required for longitudinal and temporal calculations and analyses (eg, estimates of creatinine clearance, age at start date of AE) will be based on age derived from date of birth and the date of the measurement or event, unless otherwise specified.

If a partial date for medication/ART is recorded in the eCRF, the following convention will be used to assign the medication:

- If the partial date is a start date, a ‘01’ will be used for missing days and ‘Jan’ will be used for missing months. For medications recorded separately in the eCRF as ‘Current ARV’, the latest of this imputed date or the first day of the IP (Investigational product) start will be used.
- if the partial date is a stop date, last day of the month will be used for the missing day and ‘Dec’ will be used for the missing month. For medications recorded separately in the eCRF as ‘Prior ARV’, the earlier of this imputed date or the day before the IP (Investigational product) start will be used.

HIV-1 RNA results of “No HIV-1 RNA detected” and “< 20 copies/mL HIV-1 RNA Detected” will be imputed as 19 copies/mL for analysis purposes.

HCV RNA results of “No HCV RNA detected” and “<15 IU/mL HCV RNA Detected” will be imputed as 14 IU/mL for analysis purposes.

Non-PK data (eg, Laboratory data) that are continuous in nature but are less than the lower limit of quantitation (LOQ) or above the upper LOQ will be imputed as follows:

- A value that is 1 unit less than the lower LOQ at the same precision level of the originally reported value will be used to calculate descriptive statistics if the datum is reported in the form of “< x” (where x is considered the lower LOQ). For example, if the values are reported as < 50 and < 5.0, values of 49 and 4.9, respectively, will be used to calculate summary statistics. An exception to this rule is any value reported as < 1 or < 0.1, etc. For values reported as < 1 or < 0.1, a value of 0.9 or 0.09, respectively, will be used to calculate summary statistics.
- A value that is 1 unit above the upper LOQ will be used to calculate descriptive statistics if the datum is reported in the form of “> x” (where x is considered the upper LOQ). Values with decimal points will follow the same logic as above.
- The lower or upper LOQ will be used to calculate descriptive statistics if the datum is reported in the form of “≤ x” or “≥ x” (where x is considered the lower or upper LOQ, respectively).

3.6.2. Data Handling Conventions and Transformations for PK Data

Natural logarithm transformation will be used for analyzing non-BLQ concentrations and PK parameters in intensive PK samples as applicable. Concentration values that are BLQ will be presented as “BLQ” in the concentration data listing.

Values that are BLQ will be treated as 0 at predose and postdose time points for summary purposes. The number of samples will be summarized to reflect the actual number of samples assessed at that time point.

At predose, if all concentration values are BLQ, then the mean, and order statistics (minimum, Q1, median, Q3, and maximum) will be displayed as 0 and the rest of the summary statistics (ie, SD and CV) will be missing. If any values are non-BLQ, then the number of samples, order statistics, and all summary statistics will be displayed.

At any given postdose time point, if more than one-third of the participants have a concentration value of BLQ or less than 5 participants presented at the timepoint, then only the number of samples and order statistics will be displayed; otherwise, order statistics and summary statistics will be displayed.

The following conventions will be used for the presentation of order statistics for postdose time points in the summary tables:

- If at least 1 participant has a concentration value of BLQ for the time point, the minimum value will be displayed as “BLQ.”
- If more than 25% of the participants have a concentration data value of BLQ for a given time point, the minimum and Q1 values will be displayed as “BLQ.”
- If more than 50% of the participants have a concentration data value of BLQ for a given time point, the minimum, Q1, and median values will be displayed as “BLQ.”
- If more than 75% of the participants have a concentration data value of BLQ for a given time point, the minimum, Q1, median, and Q3 values will be displayed as “BLQ.”
- If all participants have concentration data values of BLQ for a given time point, all order statistics (minimum, Q1, median, Q3, and maximum) will be displayed as “BLQ.”

Similarly, for PK concentration plotting, if more than one-third of the participants have a concentration values of BLQ or less than 5 participants presented at the timepoint, then the mean and standard deviation are not displayed at that timepoint; and if more than one-half of the participants have PK concentration values of BLQ or less than 5 participants presented at the timepoint, then the median and quartiles are not displayed at that timepoint.

3.7. Analysis Visit Windows

3.7.1. Definition of Study Day

Study Day 1 is defined as the day when the first dose of study drug (ie, B/F/TAF) was taken, as recorded on the Study Drug Administration eCRF. Study Day will be calculated from the first dosing date of study drug and derived as follows:

- For postdose study days: Assessment Date – First Dosing Date + 1
- For days prior to the first dose: Assessment Date – First Dosing Date

Last Dose Date is the latest of the study drug (B/F/TAF) end dates recorded on the Study Drug Administration eCRF form, with “Permanently Withdrawn” box checked for participants who prematurely discontinued or completed study drug according to the Study Drug Completion eCRF form.

If the date of last dose is missing (eg, only year of last dose is known or completely missing due to lost to follow-up) for participants who prematurely discontinued or completed study drug, the latest of the study drug start dates and end dates, the clinical visit dates, and the laboratory visit dates, excluding the date of 30-day follow-up visit, will be used to impute the last dose date.

Last Study Date is the latest non-missing study drug start/end date, clinic visit date, and the laboratory visit date, including the post-treatment follow-up visit date (if applicable) for participants who prematurely discontinued study or who completed study according to Study Completion eCRF form.

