## **6.6. Assessments for Early Discontinuation From Study Intervention or From the Study**

If a participant discontinues study medication dosing (eg, as a result of an AE), every attempt should be made to keep the participant in the study and continue to perform the required study-related follow-up and procedures ([Section 3.3](#)). If this is not possible or acceptable to the participant or investigator, the participant may be withdrawn from the study. The participant will be requested to return for an early study ESDD visit. If it is not possible or acceptable to the participant or investigator to keep the participant in the study (after discussion of the benefits/risks with the investigator), the participant may be withdrawn from the study and be required to return to the study site for a 30-day follow-up visit ([Table 3](#)).

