4.2.1. Duration of Exposure to Study Drug

Total duration of exposure to study drug will be defined as last dosing date minus first dosing date plus 1, regardless of any temporary interruptions in study drug administration, and will be expressed in weeks using up to 1 decimal place (eg, 4.5 weeks). If the last study drug dosing date is missing, the latest date among the study drug end date, clinical visit dates, laboratory sample collection dates, and the vital signs assessment dates that occurred during the on-treatment period will be used for that participant included in the final analyses.

The duration of exposure to study drug will be summarized using descriptive statistics (n, mean, SD, median, Q1, Q3, minimum, and maximum) and as the number and percentage of participants exposed for specified periods, eg, \geq 4 weeks (28 days), \geq 8 weeks (56 days), \geq 12 weeks (84 days), \geq 24 weeks (168 days), etc.

Summaries will be provided by overall participants for the Safety Analysis Set.

No formal statistical testing is planned.

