6.2.2. Treatment Persistence

Persistence with B/F/TAF

- Persistence with B/F/TAF at Week 12 is defined as having received B/F/TAF for \geq 57 days (i.e. the lower bound of the Week 12 visit window) and will be calculated as the proportion of participants remaining on B/F/TAF within the Week 12 analysis visit window in the FAS. Participants who prematurely discontinued from the study drug and then started the post ARV and have received B/F/TAF (including study and commercial drugs) for \geq 57 days are considered as persistence with B/F/TAF at Week 12.

- Persistence with B/F/TAF at Week 24 is defined as having received B/F/TAF for ≥ 127 days (i.e. the lower bound of the Week 24 visit window) and will be calculated as the proportion of participants remaining on B/F/TAF within the Week 24 analysis visit window in the FAS. Participants who prematurely discontinued from the study drug and then started the post ARV and have received B/F/TAF (including study and commercial drugs) for ≥ 127 days are considered as persistence with B/F/TAF at Week 24.

Non-persistence with B/F/TAF

- Non-persistence with B/F/TAF at Week 12 will be calculated as the proportion of participants who prematurely discontinue B/F/TAF by Weeks 12 Visit (ie, prematurely discontinued B/F/TAF and having received B/F/TAF for < 57 days) in the FAS.
- Non-persistence with B/F/TAF at Week 24 will be calculated as the proportion of participants who prematurely discontinue B/F/TAF by Weeks 24 Visit (ie, prematurely discontinued B/F/TAF and having received B/F/TAF for < 127 days) in the FAS.

Treatment persistence and non-persistence will be summarized. Their 2-sided 95% CIs of the proportion will be constructed based on the Clopper-Pearson exact method.

Reason for B/F/TAF premature discontinuation during the study will be listed.

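### Two SAP rules for a missing last-dose date conflict, and one of them can date the last dose to a visit made off drug

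*SAP*

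**What the plan says.** Three places in the SAP deal with a missing last-dose date.

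- **SAP 3.7.1** defines Last Dose Date. The imputation applies when, for example, "only year of last dose is known or completely missing due to lost to follow-up". It takes the latest of the drug start and end dates, clinic visits and laboratory visits, "excluding the date of 30-day follow-up visit, will be used to impute the last dose date". That is the only exclusion.
- **SAP 4.2.1**, for duration of exposure, uses a different list (it adds vital signs and omits drug start dates) and a tighter limit: "laboratory sample collection dates, and the vital signs assessment dates that occurred during the on-treatment period will be used for that participant".
- **SAP 3.5.1** sends the reader to one of these only: "For missing last dosing date of study drug, imputation rules are described in Section 4.2". It does not mention 3.7.1.

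Protocol 6.6 says that when someone stops study drug, "every attempt should be made to keep the participant in the study and continue to perform the required study-related follow-up and procedures". Footnote c of Protocol Table 3 waives the 30-day follow-up visit for those who attend a later study visit after the early study drug discontinuation (ESDD) visit.

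SAP 6.2.2 counts a participant as non-persistent at Week 12 if they "prematurely discontinued B/F/TAF and having received B/F/TAF for < 57 days"; the Week 24 cut-off is 127 days. Under SAP 6.2.1, stopping before the lower bound of an analysis window makes the participant a D=F failure at that visit.

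**The concern.** Both rules are current text, and two programmers following the SAP could derive different last-dose dates for one participant.

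The 3.7.1 rule also fits this design badly. Its single exclusion would be enough if the 30-day visit were the only contact after stopping. Here, people who stop drug are asked to keep attending scheduled visits and are then excused the 30-day visit. For them the exclusion usually removes nothing, and an off-drug Week 12 or Week 24 visit can become the imputed last dose. The rule also does not require the imputed date to fall in a year that is known.

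At stake are the persistence and D=F results, the last-dose-plus-30-days safety windows (SAP 7.2.6.1 and 7.3.2.1), and the on-treatment cuts for CD4 and participant-reported outcomes (SAP 6.3.1 and 9).

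**Working it through.** The plan gives no figure to reproduce: SAP 1.3 says that no sample size calculation was done. The check applies each rule to one participant.

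**Inputs from the documents.** Days on drug = last dose − first dose + 1 (SAP 4.2.1). Cut-offs are 57 and 127 days (SAP 6.2.2). Nominal visits are Day 28, Day 84 and Day 168 (SAP Table 3-1). Site visit windows are ±2 days through Week 12 and ±6 days at Week 24, and the ESDD visit falls within 72 hours of the last dose (Protocol Table 3). Planned n is about 35. The interval is Clopper-Pearson.

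**Assumed.** First dose on Day 1, true last dose on Day 40, stop date missing, visits attended off drug.

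Under 4.2.1, read as intended, the latest admissible date lies between the Week 4 visit (Day 28) and an ESDD visit at 40 + 3 = Day 43.

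| | True stop | 4.2.1 limit | 3.7.1, last visit Week 12 | 3.7.1, last visit Week 24 |
|---|---|---|---|---|
| Last dose (day) | 40 | 28 to 43 | 84 | 168 |
| Persistent at Week 12 (≥57 days) | no | no | yes | yes |
| Persistent at Week 24 (≥127 days) | no | no | no | yes |
| D=F discontinuation failure, Week 12 | yes | yes | no | no |
| D=F discontinuation failure, Week 24 | yes | yes | yes | no |
| Last dose + 30 | Day 70 | Day 58 to 73 | Day 114 | Day 198 |

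**Range.** Site windows move the 3.7.1 dates to Days 82–86 or 162–174, and no classification changes. A true stop anywhere from Day 30 to Day 50 gives the same pattern, since 50 + 3 = 53 is still below 57.

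**Effect at n = 35**, assuming everyone else is persistent:

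- Under 3.7.1: 0/35 = 0%, 95% CI 0 to 10.0%.
- One person correctly counted: 1/35 = 2.9%, CI 0.1 to 14.9%.
- Two people correctly counted: 2/35 = 5.7%, CI 0.7 to 19.2%.

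The D=F proportion moves by the same 2.9 points only if the off-drug HIV-1 RNA in the window is below 50 copies/mL. Otherwise the participant stays in the ≥50 group, but on the measured value rather than as a discontinuation.

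**Safety window.** With the true date, events and laboratory values after Day 70 are not treatment-emergent. With Day 84 or Day 168 imputed, those from Day 71 to the Week 12 visit enter the Week 12 co-primary counts if they meet the other criteria.

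**Rule 4.2.1 is incomplete.** It does not define the on-treatment period. Where SAP 6.3.1 and 9 define on-treatment, they use up to 1 day after the last dose date, which is circular when that date is the missing item.

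**The case against.** The case for leaving this alone has several parts.

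- **The trigger is rare.** It needs a missing stop date and continued attendance off drug. In the SAP's own example, loss to follow-up, there are no later visits, and 3.7.1 gives roughly the last contact. Those who stay have an ESDD visit, drug accountability at each visit and query resolution before the final analysis. This stands: few cases are likely.
- **SAP 3.5.1 points to the restricted rule.** This stands in part. But 3.7.1 holds the SAP's only definition of Last Dose Date, and the restricted rule lacks the definition it needs.
- **The links are inferred.** Neither SAP 6.2.2 nor the D=F rule names the imputed date, and 6.2.2 also counts commercial B/F/TAF. This stands, so the effect on those endpoints is conditional.
- **The endpoints most affected are secondary and descriptive, and listings show last-dose dates.** This stands and limits the consequence. The M=E analysis does not change, because SAP 6 keeps efficacy data collected after the last dose.

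Two stronger readings are tempting. One is that exposure in the example becomes 168/7 = 24.0 weeks instead of 40/7 = 5.7. The documents do not show this: exposure has its own rule in 4.2.1, and 3.5.1 points there. The other is that the error always flatters the drug. It does so on persistence and can on D=F, but a longer safety window adds events rather than hiding them.

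**Conclusion.** The contradiction is real, and the 3.7.1 rule gives a wrong date in a situation that the protocol encourages. When the stop date is missing or partial and visits continue off drug, it places the last dose at the latest off-drug visit. If persistence and D=F use that date, each such participant shifts non-persistence by 2.9 points at n = 35, and can shift D=F by the same amount. The safety window lengthens in the opposite, conservative direction. Exposure is unaffected provided 4.2.1 is followed, subject to its undefined on-treatment period.

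The size rests on an assumed true stop between Day 30 and Day 50 and on one or two affected participants; the documents give neither. The expected effect is small, but the text should be corrected before the SAP is finalised.

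**What to change.** Write one rule and cite it from SAP 3.5.1, 3.7.1 and 4.2.1:

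- Impute the latest study drug, visit or laboratory date that is no later than the earliest of the ESDD visit, any recorded discontinuation date, and the day before a non-study ARV regimen starts.
- Exclude every visit after known discontinuation, and stay within any known month or year.
- If none of these bounds exists, use the last date with evidence of dosing: dispensing, accountability or observed dosing.
- State that persistence, D=F, exposure and the 30-day windows all use this date, and how the commercial B/F/TAF days allowed by 6.2.2 are added.

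Two checks are needed first. The SAP mentions a Study Drug Completion eCRF but does not show that it records a discontinuation date; this should be confirmed. Protocol 6.6.1 puts the ESDD visit within 72 hours of stopping (or of notifying the investigator), while 6.6.2 puts it within 30 days, and these must be reconciled. The cap depends on it: for a Day 40 stop, 30 days allows 40 + 30 = Day 70, past the 57-day cut-off. Even at 72 hours, a stop on Days 54 to 56 could cross it (54 + 3 = 57), so a recorded discontinuation date is the better bound where one exists.

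The cost is SAP wording and one derivation, with no added work for sites. SAP Section 1 places finalisation of the SAP before database finalisation, so the change fits there.

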3.7.2. Analysis Visit Windows

Participant visits might not occur on protocol-specified days. Therefore, for the purpose of analysis, observations will be assigned to analysis windows for all analysis except PK analysis.

The analysis windows for Plasma HIV-1 RNA, Hematology, Chemistry, Urinalysis and Urine Pregnancy Laboratory Tests, Vital Signs and Weight are provided in Table 3-1.

The analysis windows for CD4+ cell count, CD4 %, estimated GFR_{CG} (Estimated GFR according to the Cockcroft-Gault formula for creatinine Clearance), and Metabolic Assessments (including fasting glucose and lipid panel: total cholesterol, high density lipoprotein [HDL], direct low density lipoprotein [LDL], triglycerides, and total cholesterol to HDL ratio) are provided in Table 3-2.

Analysis windows for the HIVTSQs are provided in Table 3-3.

HIVTSQc and Qualitative Interviews (English only) are to be completed by the participant at Week 4 with analysis window shown in Table 3-4.

A study-specific questionnaire will be completed by the participant on Day 1 (Baseline) and Week 4 with analysis window shown in Table 3-5.

Table 3-1. Analysis Visit Windows for Plasma HIV-1 RNA, Hematology, Chemistry, Urinalysis and Urine Pregnancy Laboratory Tests, Vital Signs and Weight

Visit	Study Day	Visit Window Study Day	
		Lower Limit	Upper Limit
Baseline	1	(none)	1
Week 4	28	2	56
Week 12	84	57	126
Week 24	168	127	210

Table 3-2. Analysis Visit Windows for CD4+ Cell Count, CD4 %, eGFR_{CG}, and Metabolic Assessments

Visit	Study Day	Visit Window Study Day	
		Lower Limit	Upper Limit
Baseline	1	(none)	1
Week 12	84	2	126
Week 24	168	127	210

Table 3-3. Analysis Visit Windows for HIVTSQs

Visit	Study Day	Visit Window Study Day	
		Lower Limit	Upper Limit
Baseline	1	(none)	1
Week 12	84	2	126
Week 24	168	127	210

Table 3-4. Analysis Visit Windows for HIVTSQc and Qualitative Interview

Visit	Study Day	Visit Window Study Day	
		Lower Limit	Upper Limit
Week 4	28	2	56

Table 3-5. Analysis Visit Windows for Additional Study Specific Questions

Visit	Study Day	Visit Window Study Day	
		Lower Limit	Upper Limit
Baseline		(none)	1
Week 4	28	2	56

3.7.3. PK Analysis Visits

For PK analysis, the nominal visit as recorded on the CRF will be used when data are summarized by visit.

Any data relating to unscheduled visits will not be assigned to a particular visit or time point and in general will not be included in by-visit summaries. However, the following exceptions will be made:

- An unscheduled visit prior to the first dosing of study drug may be included in the calculation of the baseline value, if applicable.

3.7.4. Selection of Data in the Event of Multiple Records in an Analysis Visit Window

Depending on the statistical analysis method, single values may be required for each analysis window. For example, change from baseline by visit usually requires a single value, whereas a time-to-event analysis would not require 1 value per analysis window.

If multiple valid, nonmissing measurements exist in an analysis window, records will be chosen based on the following rules if a single value is needed:

- For baseline, the last nonmissing value on or prior to the B/F/TAF will be selected, unless specified differently. If there are multiple records with the same time or no time recorded on the same day, the baseline value will be the average of the measurements for continuous data, or the measurement with the lowest severity for categorical data.
- For postbaseline values:
 - The record closest to the nominal day for that visit will be selected with the exception of viral load, CD4 cell counts, and CD4%, in which the latest record will be selected.
 - If there are 2 records that are equidistant from the nominal day, the later record will be selected.

- If there is more than 1 record on the selected day, the average will be taken for continuous data (except for HIV-1 RNA, see below) and the worse severity will be taken for categorical data.
- For postbaseline HIV-1 RNA, the latest (considering both date and time) record(s) in the window will be selected.
 - If both “HIV-1 RNA COBAS 6800” and “HIV RNA REPEAT COBAS” (ie, the HIV-1 RNA result obtained from an additional aliquot of the original sample) are available with the same collection time, the results from the “HIV RNA REPEAT COBAS” will be selected for analysis purposes; otherwise, if there are multiple “HIV-1 RNA COBAS 6800” records with the same collection time, the geometric mean will be taken for analysis purposes.

Since the administration of PROs is limited to specific time points, there should not be any instances of conflicting multiple baseline records. If, despite expectations, conflicting multiple baseline records occur, such instances should be queried. Instances where there are multiple records within an analysis window are handled according to the PRO guidance specified in Section 9.2.

If multiple valid nonmissing categorical observations exist in a window, records will be chosen as follows:

- For baseline, the last available record on or prior to the first dose date of study drug will be selected. If there are multiple records with the same time or no time recorded on the same day, the value with the lowest severity will be selected.
- For postbaseline visits, the most conservative value within the window will be selected.

